5.4.2 Intra-Patient Escalation

Intra-patient dose escalation is not allowed.

5.5 **Grading of Adverse Events**

Adverse events (toxicities) will be graded according to the NCI Common Terminology Criteria for Adverse Events (CTCAE) version 5.0. All appropriate treatment areas should have access to a copy of the CTCAE version 5.0. A copy of the CTCAE version 5.0 can be downloaded from the CTEP website (http://ctep.cancer.gov/protocolDevelopment/electronic_applications/ctc.htm). Any suspected or confirmed dose-limiting toxicity should be reported immediately (within 24 hours) to the Study Chair.

5.6 **Definition of Dose-Limiting Toxicity (DLT)**

DLT will be defined as any of the following events that are possibly, probably or definitely attributable to protocol therapy. The DLT observation period for the purposes of dose-confirmation will be the first cycle of therapy.

Dose limiting hematological and non-hematological toxicities are defined differently.

5.6.1 Non-hematological dose-limiting toxicity:

5.6.1.1 All Grade 3 or greater non-hematological toxicity not clearly related to the underlying disease and attributable to protocol therapy will be considered a DLT except:

- Grade 3 or 4 elevation of ALT/AST that returns to Grade ≤ 1 within 14 days. NOTE: For the purposes of this study the ULN for ALT is defined as 45 U/L regardless of baseline and for AST is defined as 50 U/L regardless of baseline. See [Appendix III](#) for values that represent thresholds between CTCAE grades.

THIS PROTOCOL IS FOR RESEARCH PURPOSES ONLY, SEE PAGE 1 FOR USAGE POLICY

- Grade 3 or 4 electrolyte abnormalities that resolve, with or without supplementation intervention, to \leq Grade 2 within 72 hours. Electrolyte supplementation is encouraged.
- Grade 3 arthralgia/myalgia that returns to Grade \leq 2 within 5 days on analgesics
- Grade 3 or 4 fever, febrile neutropenia, or infection with or without hospitalization
- Grade 3 tumor lysis syndrome
- Alopecia
- Grade 3 maculo-papular or morbilliform rash that resolves to \leq Grade 2 within 7 days
- Grade 3 mucositis that resolves (with or without supportive care) to \leq Grade 2 within 14 days
- Grade 3 fatigue or anorexia responsive to supportive care within 7 days
- Grade 3 nausea, vomiting, and/or diarrhea responsive to supportive care within 72 hours
- Early intervention with TPN or enteral tube feeding for anorexia, nausea, or concern for poor nutritional status

5.6.2 Hematological dose-limiting toxicity:

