6.2 Dose Modifications for Non-Hematological Toxicity

6.2.1 Patients will have ALT/AST/bilirubin evaluated prior to each planned dose of MLN4924 (pevonedistat) in order to determine whether the scheduled dose

should be administered. It is anticipated that ALT and AST may be elevated for approximately 48 hours following the end of the 1st MLN4924 (pevonedistat) infusion.

NOTE: See [Appendix III](#) for toxicity grading table.

If a patient experiences > Grade 3 elevation of ALT/AST on or after Cycle 1, Day 1 then the Cycle 1, Day 3 MLN4924 (pevonedistat) dose should not be given. If ALT/AST returns to \leq Grade 1 or baseline values by Day 5 then the patient should receive their Day 5 MLN4924 (pevonedistat) dose and this will not be considered a DLT. If ALT/AST does not return to \leq Grade 1 or baseline values by Day 5 then MLN4924 (pevonedistat) should be held and this will be considered a DLT. Persistent elevations of ALT/AST > Grade 2 beyond 2 days between any other doses after Cycle 1, Day 1 will be considered a DLT.

6.2.2 Patients who experience a dose limiting toxicity during cycle 1 that resolves to baseline or < Grade 1 at the time of next cycle can proceed with the next cycle at dose level -1.

6.3 **Modifications and Supportive Care Recommendations for Toxicity Related to Protocol Therapy (Cycle 1 and Cycle 2)**

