If a patient experiences \geq Grade 3 elevation of ALT/AST/bilirubin that does not return to \leq Grade 1 or baseline prior to the next dose of MLN4924 (pevonedistat), the dose will be held and this will be considered a DLT. However, patients can still receive azacitidine as scheduled and can receive subsequent fludarabine and cytarabine if ALT \geq Grade 3 after discussion with study chair. NOTE: See [Appendix III](#) for values that represent thresholds between CTCAE grades.

Patients who experience a dose limiting toxicity during cycle 1 that resolves to baseline or \leq Grade 1 at the time of next cycle can proceed with the next cycle at dose level -1.

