11.2.2 Maximum Tolerated Dose

- The MTD will be the maximum dose at which fewer than one-third of patients experience DLT (See [Section 5.6](#)) during Cycle 1 of therapy.
- In the unlikely event that two DLTs observed out of 6 evaluable patients are different classes of Adverse Effects (e.g. hepatotoxicity and myelosuppression), AND all of the following conditions are met, expansion of the cohort to 12 patients will be considered:
 - One of the DLTs does not appear to be dose and/or drug-related
 - The Adverse Effects are readily reversible
 - The study chair, DVL statistician, DVL committee chair or vice chair, and IND sponsor all agree that expansion of the cohort is acceptable
- The DLTs observed in the pharmacokinetic (PK) expansion cohort will be counted towards the total number of DLTs observed at the RP2D/MTD during the dose confirmation portion of the study. If $\geq 1/3$ of the cohort of patients at the RP2D/MTD (during the dose confirmation plus the PK expansion) experience DLT then the MTD will be exceeded.

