11.3 Dose Confirmation and Determination of MTD/RP2D

The rolling six phase 1 trial design will be used for the conduct of this study.³² There is no dose escalation beyond DL1 (20 mg/m²); but the R6 logic will be used to determine the MTD/RP2D. DL1 will be defined as the RP2D if there are less than or equal to 1 patient(s) with a DLT among up to six evaluable patients. Otherwise, DL-1 will open to accrual of up to six evaluable patients. DL-1 will be defined as the MTD/RP2D if there are less than or equal to 1 patient(s) with a DLT among six evaluable patients. Otherwise, DL-1 will have exceeded the MTD and the study will close to accrual without having defined an MTD/RP2D.

In addition to determination of the RP2D/MTD, a descriptive summary of all toxicities will be reported.

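### Sections 5.6.1.1, 6.2.1 and 6.3.5 give different DLT verdicts on the same transient Grade 3-4 ALT/AST rise in Cycle 1

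*Combined protocol and SAP*

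**What the plan says.** Three sections of the combined protocol and SAP classify a Grade 3-4 ALT/AST rise in Cycle 1.

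- **Section 5.6.1.1** lists as an exception to non-hematological DLT a "Grade 3 or 4 elevation of ALT/AST that returns to Grade" 1 or less within 14 days. It sets no condition about the next dose and does not refer to Section 6.
- **Section 6.2.1** applies to a "Grade 3 elevation of ALT/AST on or after Cycle 1, Day 1", with a strict greater-than sign printed before the grade. The Day 3 dose is omitted. If values are at Grade 1 or less, or baseline, by Day 5, the patient receives the Day 5 "dose and this will not be considered a DLT". If not, pevonedistat "should be held and this will be considered a DLT". A further sentence makes elevations above Grade 2 that last more than 2 days between other doses a DLT.
- **Section 6.3.5** applies at Grade 3 or more. If the value is not back to Grade 1 or less, or baseline, before the next pevonedistat dose, "the dose will be held and this will be considered a DLT". It has no exception for Day 3.

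The label is then used in two places. Section 11.3 says "DL1 will be defined as the RP2D if there are less than or equal to 1 patient(s) with a DLT"; the denominator there is at most six evaluable patients. Sections 6.2.2 and 6.3.5 say that a patient whose Cycle 1 DLT resolves "can proceed with the next cycle at dose level -1". Section 11.2.2 states "The MTD will be the maximum dose at which fewer than one-third of patients experience DLT" and refers to Section 5.6 for the definition.

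**The concern.** A DLT definition has to give one answer per patient, fixed before the data are seen. Here the answer depends on which section is read, for any rise that outlasts the next scheduled pevonedistat dose but clears within 14 days.

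The situation is foreseeable. Section 6.2.1 itself expects ALT/AST to be raised for about 48 hours after the first infusion (it gives no grade), and that is when the Day 3 check falls. In the adult azacitidine combination study described in Section 2.3.1, both DLTs at 20 mg/m² were transaminase elevations that resolved.

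The count is small, so one patient matters:

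- Two DLTs in six at Dose Level 1 open Dose Level -1; two there close the study (Section 11.3).
- Under Section 11.1, two DLTs in the first three patients force de-escalation, and one in the first two imposes a 30-day wait after the third patient's first dose.
- DLTs in the PK expansion are added to the count (Section 11.2.2).
- The patient's own Cycle 2 dose depends on the label.
- A patient not counted as a DLT who missed one of three doses has had 2/3 = 67% of planned pevonedistat, against the 85% required by Section 11.2.1. Depending on the reading, that patient could be a DLT, an evaluable non-DLT, or replaced.

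**Working it through.** **Step 1. Apply each rule to the same patient.** Pevonedistat is given on Days 1, 3 and 5. Assume the rise starts on Day 2 and is attributable to protocol therapy.

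| Course of ALT/AST | 5.6.1.1 | 6.2.1 | 6.3.5 |
|---|---|---|---|
| Grade 1 or less before the Day 3 dose | no DLT | no DLT | no DLT |
| Grade 4 at Day 3, Grade 1 by Day 5 | no DLT | no DLT | DLT |
| Grade 4 on Days 2-4, Grade 2 on Day 5, Grade 1 by Day 9 | no DLT | DLT | DLT |
| Grade 3 at Day 3, Grade 1 by Day 5 | no DLT | Day 3/Day 5 rule not triggered, read literally | DLT |
| Grade 4, still raised beyond 14 days | DLT | DLT | DLT |

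Row 2 sets 6.2.1 against 6.3.5, row 3 sets 5.6.1.1 against 6.2.1, and rows 2 to 4 set 5.6.1.1 against 6.3.5. Every pair conflicts somewhere.

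**Step 2. Does the allowance for recovery to baseline help?** Section 4.1.5.2 caps ALT and AST at 2.5 × ULN.

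- ALT: 2.5 × 45 = 112.5 U/L, below the top of Grade 1 (135 U/L, Appendix III).
- AST, using the Appendix III ULN: 2.5 × 50 = 125 U/L, below the top of Grade 1 (150 U/L).

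An eligible baseline is already Grade 1 or less, so the allowance changes nothing.

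**Step 3. Effect on the six-patient rule.** The plan gives no operating characteristics for its DLT rule, so there is no figure to reproduce on this point. Its enrolment ceilings do reproduce (18/0.8 = 22.5, rounded up to 23; 30/0.8 = 37.5, rounded up to 38) and are not affected.

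Let p be the chance that a patient has a disputed event. With six evaluable patients, P(2 or more) = 1 − (1−p)^6 − 6p(1−p)^5 and P(1 or more) = 1 − (1−p)^6. The only nearby rate is 2/55 = 3.6% at 20 mg/m² in adults (Section 2.3.1), with an exact upper 95% limit of 12.5%. The other rates are assumptions.

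| p | P(2 or more of 6), this cause alone |
|---|---|
| 3.6% (2/55) | 1.8% |
| 10% (assumed) | 11.4% |
| 12.5% (upper limit for 2/55) | 16.7% |
| 20% (assumed, above that limit) | 34.5% |
| 30% (assumed, above that limit) | 58.0% |

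Under 5.6.1.1 each of these is 0. One event uses up the single DLT allowed: P(1 or more) is 19.9% at 3.6% and 46.9% at 10%.

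**Step 4. Add other DLTs.** Assume other DLTs occur independently in q = 10% of patients. The total rate is 1 − (1−q)(1−p).

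- Not counted (5.6.1.1): rate 10%, P(2 or more) = 11.4%.
- Counted, p = 3.6%: rate 1 − 0.90 × 0.964 = 13.3%, P(2 or more) = 18.4%.
- Counted, p = 10%: rate 1 − 0.90 × 0.90 = 19%, P(2 or more) = 32.0%.

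Varying q: at 5%, the chance is 3.3% not counted, against 8.5% and 21.2% counted. At 20%, it is 34.5% not counted, against 41.6% and 53.6% counted.

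If q = 10% and the same rates held at Dose Level -1, the chance that both levels fail is the square: 0.114² = 1.3% not counted, against 0.184² = 3.4% and 0.320² = 10.2% counted.

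**The case against.** The best reply is that Section 5.6 governs. It is the titled DLT definition, it sets the observation period for dose confirmation, and Section 11.2.2 cites it for the MTD. Sections 6.2.1 and 6.3.5 sit under dose modification, and no counting rule cites them. This favours 5.6.1.1 but does not settle the matter. Both Section 6 rules state a DLT verdict outright, and nothing limits those verdicts to dosing. If 5.6.1.1 alone decided, the 6.2.1 statement that recovery by Day 5 is no DLT would be redundant, because such recovery already falls within 14 days.

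A second reply reads the specific rule over the general: 6.3.5 adds a pre-dose criterion and 6.2.1 is a Day 3 exception to it. That gives one answer per case, but the text does not state it, and it departs from Section 5.6. With the 6.2.1 trigger read literally, it also produces an inversion: Grade 4 at Day 3 (ALT above 900 U/L) that recovers by Day 5 is excused, while Grade 3 (226-900 U/L) with the same recovery counts. The inversion does not arise under any one section alone.

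The strict greater-than sign may be a lost underline. Section 6.2.2 has a strict less-than sign where the matching sentence in 6.3.5 has less-than-or-equal. This is possible but unproven. If so, the trigger mismatch disappears; rows 2 and 3 of the table stand.

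Several limits on the consequences do stand. No section directs pevonedistat through a Grade 3-4 rise, so the dispute is about the label. Section 2.3.2 reports a similar pharmacodynamic pattern at 15 and 20 mg/m². Study Chair entry and the weekly review limit inconsistency between sites, though they supply no rule. The only document-based rate gives about 2% from this cause alone.

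**Conclusion.** The concern holds. For Grade 3-4 ALT/AST rises that outlast the next scheduled dose and clear within 14 days, the plan as written gives contradictory DLT verdicts, and these feed the RP2D decision and the Cycle 2 dose. It should be fixed before the rule is applied.

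The contradiction rests on the text alone. Its numerical size rests on assumptions: the event rate on this pediatric four-drug regimen is unknown, 2/55 comes from adults on a different combination with a DLT definition not shown, and the 10% rate for other DLTs is illustrative. On those terms the chance that Dose Level 1 fails moves from 11% to between 18% and 32%. The calculation covers the six-patient cohort only, not the PK expansion.

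**What to change.** State the ALT/AST rule once, in Section 5.6.1.1: trigger grade, recovery level (Grade 1 or less, or baseline), time window, and any pre-dose non-recovery criterion the sponsor wants to keep. Delete the DLT verdicts from 6.2.1 and 6.3.5 so that they govern dose holding only and refer to 5.6.1.1 for DLT status. Use the same trigger, either Grade 3 or more or Grade 4 only, in both. The choice of trigger and window is the sponsor's clinical decision. In the same amendment, say how a protocol-directed omitted dose counts toward the 85% requirement in Section 11.2.1.

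The cost is a wording amendment. No tests are added, because ALT, AST and bilirubin are already required before every pevonedistat dose (Section 8.1), and enrolment is unchanged.

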6.0 DOSE MODIFICATIONS FOR ADVERSE EVENTS

The Study Chair must be notified of any dosage modification. Patients may receive up to 2 cycles of chemotherapy.

6.1 Dose Modifications for Hematological Toxicity

6.1.1 Patients who experience a hematologic dose limiting toxicity (see [Section 5.6.2](#)), defined as failure to recover peripheral ANC $> 500/\text{uL}$ and non-transfusion dependent platelet count $> 20,000/\text{uL}$ due to documented bone marrow aplasia/hypoplasia (not due to malignant infiltration or Grade 3 infection) for greater than or equal to 50 days from the start of fludarabine and cytarabine administration, will be allowed to proceed at the discretion of the treating physician and study chair with cycle 2 at MLN4924 (pevonedistat) dose level -1. The patient's dose for azacitidine, fludarabine, and cytarabine will remain unchanged.

6.2 Dose Modifications for Non-Hematological Toxicity

6.2.1 Patients will have ALT/AST/bilirubin evaluated prior to each planned dose of MLN4924 (pevonedistat) in order to determine whether the scheduled dose

should be administered. It is anticipated that ALT and AST may be elevated for approximately 48 hours following the end of the 1st MLN4924 (pevonedistat) infusion.

NOTE: See [Appendix III](#) for toxicity grading table.

If a patient experiences > Grade 3 elevation of ALT/AST on or after Cycle 1, Day 1 then the Cycle 1, Day 3 MLN4924 (pevonedistat) dose should not be given. If ALT/AST returns to \leq Grade 1 or baseline values by Day 5 then the patient should receive their Day 5 MLN4924 (pevonedistat) dose and this will not be considered a DLT. If ALT/AST does not return to \leq Grade 1 or baseline values by Day 5 then MLN4924 (pevonedistat) should be held and this will be considered a DLT. Persistent elevations of ALT/AST > Grade 2 beyond 2 days between any other doses after Cycle 1, Day 1 will be considered a DLT.

6.2.2 Patients who experience a dose limiting toxicity during cycle 1 that resolves to baseline or < Grade 1 at the time of next cycle can proceed with the next cycle at dose level -1.

6.3 **Modifications and Supportive Care Recommendations for Toxicity Related to Protocol Therapy (Cycle 1 and Cycle 2)**

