An additional trial evaluating MLN4924 (pevonodistat) in combination with azacitidine in older adult patients (≥ 60 years of age) with de novo AML has demonstrated an acceptable toxicity profile. This study administered azacitidine IV or subcutaneously for a total of 7 days on days 1-5, 8-9 (5 on/2 weekend off/2 on) at a dose of 75 mg/m^2 with MLN4924 (pevonodistat) administered on days 1, 3, and 5 in 28-day treatment cycles. MLN4924 (pevonodistat) doses of 20 mg/m^2 (n=55) and 30 mg/m^2 (n=6) dosing were evaluated and the MTD was determined to be 20 mg/m^2 . A total of 61 patients have been treated on this study, receiving a median of 4 cycles of therapy (range of 1-33). The most common AEs were constipation (48%), nausea (42%) fatigue (42%), and anemia (39%). A majority of patients (n=53, 83%) experienced a \geq grade 3 AE, with most common being anemia and febrile neutropenia (30% each), thrombocytopenia (23%), neutropenia (20%), and pneumonia (17%). There were DLTs observed in four patients (n=2 at 20 mg/m^2 and n=2 at 30 mg/m^2). One patient had elevated bilirubin, and the other 3 patients had elevated AST and ALT (maximum grade 3-4). For the 2 patients with transaminase elevation treated at the 20 mg/m^2 dose, this was a transient effect

that resolved spontaneously and the patients were successfully re-challenged at a lower dose and remained on study. The most common SAEs detected were febrile neutropenia (25%) and pneumonia (14%). These infectious events and myelosuppression are commonly observed in AML regimens. None of the on-study deaths (n=11) were attributed to MLN4924 (pevoneditat). A total of 64 patients were treated and included in the intent to treat (ITT) cohort, with a total of 52 patients evaluable for response. Among the ITT cohort, the CR/CRI rate was 39% (20 CR, 5 CRI) with 7 PRs for an overall response rate (ORR) of 50%. Among the patients evaluable for response, a CR/CRI rate of 48% was observed.⁶

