4.1.5 Organ Function Requirements

4.1.5.1 Adequate Renal Function Defined as:

- Creatinine clearance or radioisotope GFR $\geq 60\text{ml/min}/1.73\text{ m}^2$ or
- A serum creatinine based on age/gender as follows:

Age	Maximum Serum Creatinine (mg/dL)	
	Male	Female

THIS PROTOCOL IS FOR RESEARCH PURPOSES ONLY, SEE PAGE 1 FOR USAGE POLICY

1 month to < 6 months	0.4	0.4
6 months to < 1 year	0.5	0.5
1 to < 2 years	0.6	0.6
2 to < 6 years	0.8	0.8
6 to < 10 years	1	1
10 to < 13 years	1.2	1.2
13 to < 16 years	1.5	1.4
≥ 16 years	1.7	1.4

The threshold creatinine values in this Table were derived from the Schwartz formula for estimating GFR (Schwartz et al. J. Peds, 106:522, 1985) utilizing child length and stature data published by the CDC.

4.1.5.2 Adequate Liver Function Defined as:

- Bilirubin (sum of conjugated + unconjugated) \leq upper limit of normal (ULN) for age.
- Alanine aminotransferase (ALT) and aspartate aminotransferase (AST) $\leq 2.5 \times$ ULN. For the purpose of this study, the ULN for SGPT is 45 U/L.

4.1.5.3 Adequate Cardiac Function Defined As:

- Shortening fraction of $\geq 27\%$ by echocardiogram, or
- Ejection fraction of $\geq 50\%$ by echocardiogram or radionuclide angiogram
- No ventricular or supraventricular arrhythmia on EKG
- Prolonged rate corrected QT (QTc) interval < 500 msec

4.1.5.4 Adequate Pulmonary Function Defined As:

- Pulse oximetry $> 94\%$ on room air if there is clinical indication for determination (e.g. dyspnea at rest)

4.1.5.5 Adequate Coagulation Defined As:

- INR ≤ 1.5

4.1.5.6 Adequate Bone Marrow Function Defined As:

- Hemoglobin > 8.0 g/dL (may receive RBC transfusions)

4.1.6 Informed Consent: All patients and/or their parents or legally authorized representatives must sign a written informed consent. Assent, when appropriate, will be obtained according to institutional guidelines.

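### Sections 6.2.1 and 6.3.5 set different triggers for withholding the Cycle 1 Day 3 pevonedistat dose, and neither says which governs

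*Combined protocol and SAP*

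**What the plan says.** Three places in the protocol bear on liver enzymes around the Day 3 dose.

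- **Section 6.2.1** has ALT, AST and bilirubin checked before every pevonedistat dose so that the site can decide whether to give it. It expects ALT and AST to be raised for about 48 hours after the first infusion. Its Day 3 rule begins "If a patient experiences > Grade 3 elevation of ALT/AST on or after Cycle 1, Day 1 then the Cycle 1, Day 3" and concludes that this dose is not given. If values are back to Grade 1 or baseline by Day 5, "then the patient should receive their Day 5 MLN4924 (pevonedistat) dose and this will not be considered a DLT". If they are not, the drug is held and the event is a DLT. A last sentence covers elevations above Grade 2 lasting more than 2 days "between any other doses after Cycle 1, Day 1 will be considered a DLT".
- **Section 6.3.5**, under a heading that covers both cycles, addresses an elevation at or above this level: "Grade 3 elevation of ALT/AST/bilirubin that does not return to" Grade 1 or baseline before the next dose. Its consequence is "the dose will be held and this will be considered a DLT". It makes no exception for Day 3.
- **Section 5.6.1.1** exempts Grade 3 or 4 ALT/AST from the DLT definition if the value returns to Grade 1 or lower within 14 days.

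Neither 6.2.1 nor 6.3.5 refers to the other.

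**The concern.** Section 6.2.1 presents itself as the rule by which the scheduled dose is given or not, yet its Day 3 trigger lies a full grade above the one in 6.3.5. The two also treat recovery differently. 6.2.1 looks at whether the elevation occurred at all; 6.3.5 looks at whether it has resolved. A site working from one section can therefore act differently from a site working from the other.

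The timing makes this more than a drafting detail. If doses are given at the same clock time, the Day 3 infusion starts 48 − 1 = 47 hours after the end of the 1-hour Day 1 infusion. That is inside the window in which 6.2.1 itself expects raised enzymes. Hepatic events also accounted for all four DLTs in the adult azacitidine combination study in Section 2.3.1: "One patient had elevated bilirubin, and the other 3 patients had elevated AST and ALT".

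At stake are one of three pevonedistat doses in the cycle (33%), whether the Day 5 PK samples follow two earlier doses or one, and a DLT label that 6.3.5 attaches to the hold. Section 11.3 tolerates at most one patient with a DLT among up to six.

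**Working it through.** The plan states no figure on this point, so the check sets the rules side by side.

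**Grade limits.** Appendix III fixes the ULN at 45 U/L for ALT and 50 U/L for AST. The upper limits of Grades 1, 2 and 3 are 3, 5 and 20 × ULN:

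- ALT: 3 × 45 = 135; 5 × 45 = 225; 20 × 45 = 900. Grade 3 is 226–900 U/L.
- AST: 3 × 50 = 150; 5 × 50 = 250; 20 × 50 = 1000. Grade 3 is 251–1000 U/L.

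**Rules applied to the Day 3 decision (ALT/AST).** The middle column shows what follows if the printed sign was meant as at or above Grade 3.

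| State before the Day 3 dose | 6.2.1 as printed | 6.2.1 if at or above was meant | 6.3.5 |
|---|---|---|---|
| Never above Grade 2 | no omission | no omission | no hold |
| Still Grade 3 | no omission | omit | hold, DLT |
| Grade 3 earlier, now Grade 2 | no omission | omit | hold, DLT |
| Grade 3 earlier, now Grade 1 or baseline | no omission | omit | no hold |
| Still Grade 4 | omit | omit | hold, DLT |
| Grade 4 earlier, now Grade 2 or 3 | omit | omit | hold, DLT |
| Grade 4 earlier, now Grade 1 or baseline | omit | omit | no hold |

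As printed, the sections differ in the second, third and last rows. With the other sign they differ in the fourth and last rows, the recovered cases. The second row needs only the reading that is already required before each dose. The recovered cases arise only if an extra test is done between doses.

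**Does the baseline exit in 6.3.5 remove the conflict?** No. Section 4.1.5.2 caps both enzymes at 2.5 × ULN. For ALT that is 2.5 × 45 = 112.5 U/L; for AST, with the study ULN, 2.5 × 50 = 125 U/L. Both lie within Grade 1. Section 4.1.5.2 fixes the ULN only for ALT. An eligible AST could reach Grade 3 only if the site's own ULN exceeded 250 / 2.5 = 100 U/L.

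**Does another sentence in 6.2.1 fill the gap?** No. The sentence on persistence above Grade 2 is about intervals other than the one before Day 3, and it assigns a DLT label without deciding a dose.

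**Frequency, by assumption only.** The documents give no rate of Grade 3 ALT/AST at Day 3. For an assumed rate r, the chance of at least one such child among six is 1 − (1 − r)^6.

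- r = 2/55 = 3.6%: 1 − (53/55)^6 = 0.20. This is the adult transaminase DLT rate at 20 mg/m² in Section 2.3.1, not a Day 3 Grade 3 rate.
- r = 5%: 1 − 0.95^6 = 0.26.
- r = 20%: 1 − 0.80^6 = 0.74.

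**The case against.** The best reply is that there is no outright contradiction. Section 6.2.1 names one circumstance in which the Day 3 dose is omitted and is silent below it; 6.3.5 then adds a hold at unrecovered Grade 3. A site that obeys both holds the dose and breaks neither. This stands as far as it goes. A reader might infer that the protocol instructs dosing at Grade 3, and the text does not say that. But 6.2.1 describes its tests as the basis for the dosing decision, and no cross-reference sends its reader to 6.3.5. Nor would the Study Chair notification in Section 6.0 catch a difference, since it concerns dosage modifications and a full dose is not one.

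The sign itself may also be a misprint or a PDF reading error. The sentence about continuing after a Cycle 1 DLT appears with a strict inequality in 6.2.2 and a non-strict one in 6.3.5, which suggests that equality bars were lost in 6.2. On the other hand, non-strict signs are printed elsewhere in 6.2.1. If the bar was lost, the disagreement at unrecovered Grade 3 goes away. The disagreement over recovered elevations remains.

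Two further inferences are tempting and do not hold:

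- **Evaluability.** Two of three doses is 67%, below the 85% in Section 11.2.1, so one might expect this child to be replaced. Under 6.2.1 no dose is missed. Under 6.3.5 the hold is a DLT, and 11.2.1 replaces only patients without one.
- **Bilirubin.** Section 6.2.1 orders the test without a dosing condition, but 6.3.5 supplies one. That is a gap filled elsewhere, not a second conflict.

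**Conclusion.** The concern holds as a mismatch of triggers. It spans the whole Grade 3 band (ALT 226–900, AST 251–1000 U/L) on the text as printed, and it affects one of three pevonedistat doses in Cycle 1. If the sign in 6.2.1 has lost its equality bar, the mismatch shrinks to elevations that have recovered before Day 3.

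The DLT label is tied to it. Even where both sections withhold, 6.3.5 counts a DLT at the hold, 6.2.1 waits until Day 5, and 5.6.1.1 allows 14 days. With at most one DLT permitted in up to six patients, a single child handled differently could alter the dose decision. How likely that is cannot be established: the 20% to 74% above rests on assumed rates and should not be quoted as an expected frequency. The case for correction is that the instruction bears on patient safety and DLT counting and is cheap to repair.

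**What to change.** Reconcile 6.2.1 and 6.3.5, together with the ALT/AST exception in 5.6.1.1, so that there is one hold threshold and one recovery condition for ALT, AST and bilirubin before each pevonedistat dose. State it in one section, have the other refer to it, and say there when a hold counts as a DLT. If Day 3 is meant to have its own rule, label it as an exception and state whether recovery before the dose matters. Check the inequality signs in 6.2.1 and 6.2.2 against the source file at the same time. Which threshold applies is for the sponsor to decide.

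The cost is protocol wording in these sections. No tests are added, because ALT, AST and bilirubin must already be read before each dose under Section 8.1.
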